6.1 Target sample size

The number of subjects registered in the treatment period will be 20.

Rationale

The proportion of patients who are not treated with any ESA formulation is as small as approximately 10% of all hemodialysis-dependent patients in Japan. Patients receiving any ESA formulation are allowed to register after undergoing a washout; however, the number of eligible patients was thought to be very limited when considering the selection/exclusion criteria. Therefore, the target sample size was set to 20 after consideration of feasibility.

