- ✓ Dosage increases should be performed at intervals of at least 4 weeks in principle, and dosage decreases at intervals of at least 2 weeks.
- ✓ If Hb levels suddenly increase (>2.0 g/dL change in the past 4 weeks*), decrease MT-6548 dosage by 1 tablet.
- ✓ The MT-6548 Tablet dose should be increased by 1 tablet if Hb levels are <10.0 g/dL. However, decrease by 1 tablet instead of increasing in cases of sudden increase in Hb (more than 2.0 g/dL change in past 4 weeks*).
- ✓ The MT-6548 Tablet dose should be decreased by 1 tablet if Hb levels are >11.5 g/dL.
- ✓ If Hb levels are >12.0 g/dL and ≤13.0 g/dL with a rapid increase in Hb levels (>2.0 g/dL change in the past 4 weeks*), MT-6548 tablet administration should be discontinued, and the dose should be decreased by 1 tablet and MT-6548 tablet administration resumed after Hb levels decrease to ≤12.0 g/dL.
- ✓ If Hb levels are >13.0 g/dL, MT-6548 tablet administration should be discontinued, and the dose should be decreased by 1 tablet and MT-6548 tablet administration resumed after Hb levels decrease to ≤12.0 g/dL.

*The rate of increase in Hb levels will be calculated using the Hb levels at the time points closest to 4 weeks among those measured 3–5 weeks prior to the day of dosage adjustment. A rate of change greater than 0.5 g/dL/week will be regarded as a rapid increase in Hb levels. If no Hb levels were measured 3–5 weeks prior to the day of dosage adjustment,

the Hb levels measured at most recent time points prior to 5 weeks before the day of dosage adjustment will be used to calculate the rate of increase in Hb levels.

(3) Administration method

The study drug is taken once-daily orally. The drug does not need to be taken with meals, but timing should be as consistent as possible throughout the treatment period, both in relation to meals and time of day. (The first dose will be taken after required tests are finished on the first day of the treatment period.)

Rationale

[REDACTED]

The dosage adjustment algorithm was set in order to avoid excessive Hb increase with reference to target Hb values in nephrogenic anaemia therapy according to JSDT's "Guideline for Renal Anemia in Chronic Kidney Disease 2015."

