## 7. Statistical Method

### 7.1 Basic Matters

#### 7.1.1 Level of significance and confidence coefficient

When implementing tests, level of significance should be set at 2-sided 5%. Confidence interval (CI) will be 2-sided with a confidence coefficient of 95%.

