### 7.5.1 Analysis of primary endpoint

(1) Mean Hb values at Week 20 and Week 24 of the treatment period

Descriptive statistics should be calculated for the primary efficacy endpoint of the mean Hb values at Week 20 and Week 24 of the treatment period. The MMRM is used to model the mean Hb values at each evaluation time point based on the following model, and the mean Hb values for Week 20 and Week 24 of the treatment period should be obtained, and the least squares mean (LSMean), its standard error, and 2-sided 95% CIs for the mean Hb values should be calculated.

[MMRM Model]

- Covariate: Response variable value of the first day of the treatment period
- Fixed effects: Evaluation time point
- Degrees of freedom adjustment: Kenward-Roger method
- Covariance matrix within subject for each subject: Unstructured (type = UN; unstructured)

If the variance-covariance matrix within subjects is not converged using unstructured data, the variance-covariance matrix within subjects should be changed in the following order, and the analysis should be performed using the variance-covariance matrix within subjects that converges first.

Heterogeneous Toeplitz (TOEPH) → Heterogeneous AR (1) (ARH [1]) → Heterogeneous CS (CSH) → Toeplitz (TOEP) → First-order autoregressive (AR [1]) → Compound symmetry (CS)

➤ Random effects: Subjects

(2) Hb values at each evaluation time point in the treatment period

Hb value and change of Hb from the first day of the treatment period at each evaluation time point of the treatment period should be obtained, and its descriptive statistics should be calculated. Before and after comparison will be conducted for changes of Hb from the first day of the treatment period to each evaluation time using the paired t-test.

LSMean, its standard errors, and 2-sided 95% CI of mean Hb values at each evaluation time point of the treatment period should be calculated using the MMRM model (with compound symmetry [CS] for a variance-covariance matrix within subjects) similar to that used in “mean Hb values at Week 20 and Week 24 of the treatment period”.

Furthermore, LSMean, its standard errors, and 2-sided 95% CI of the change from the first day of the treatment period should be calculated at each evaluation time point of the treatment period using the MMRM (with compound symmetry [CS] for a variance-covariance matrix within subjects).

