### 7.5.2 Analysis of other endpoints

(1) Changes in mean Hb values from the first day of the treatment period at Week 20 and Week 24 of the treatment period

Descriptive statistics for change from Hb value on the first day of the treatment period to mean Hb values at Week 20 and Week 24 in the treatment period should be calculated. A paired t-test should be performed for before and after comparison of changes from the first day of the treatment period. The analysis should be conducted using the MMRM model (with compound symmetry [CS] for a variance-covariance matrix within subjects). LSMeans, its standard errors, and 2-sided 95% CI for change from Hb value on the first day of the treatment period to mean Hb values at Week 20 and Week 24 of the treatment period should be calculated.

(2) Proportion of subjects with a  $\geq 1.0$  g/dL increase in mean Hb values from the first day of the treatment period at each time point of the treatment-period.

The number, proportion, and 95% CI (Clopper-Pearson [exact] method) of the proportion of subjects with a mean Hb increase of  $\geq 1.0$  g/dL from the first day to each evaluation time point of the treatment period should be provided.

(3) Proportion of subjects who received ESA rescue therapy, blood transfusion, or phlebotomy

The number, proportion of subjects and 95% CI (Clopper-Pearson [Exact] method) of the proportion of subjects receiving rescue therapy with an ESA formulation should be provided, after the first day of the treatment period, in each period between scheduled study visits and during the entire treatment period from the first day to Week 24 of the treatment period.

The analyses same to the above subjects receiving rescue therapy with ESA formulation should be performed for subjects receiving rescue therapy with RBC transfusion or receiving phlebotomy.

(4) Study drug dosage

1) Study drug dosage

Descriptive statistics of mean daily dose should be calculated for each scheduled study visit from the first day of the treatment period up to treatment period Week 24. The time course diagram for mean daily dose should be separately prepared. 95% CI of the mean will be represented by an error bar. Each period between scheduled study visits is defined as the period between the scheduled visit and the day before the next scheduled study visit.

2) Distribution of dose of MT-6548 tablets

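### Compound symmetry is fixed for Hb and Hb change at each visit, so one variance serves all nine visits and the intervals are miscalibrated if the spread of Hb differs between visits

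*SAP*

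**What the plan says.** SAP 7.5.1 deals with the Hb measurements in two ways.

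- **Item (1), mean of Weeks 20 and 24.** The model specifies "Covariance matrix within subject for each subject: Unstructured (type = UN; unstructured", then six fallbacks in order: TOEPH, ARH(1), CSH, TOEP, AR(1), CS. The first three allow a different variance at each visit, and CS comes last. The first-day value is a covariate, and the list includes "Degrees of freedom adjustment: Kenward-Roger method".
- **Item (2), Hb at each time point.** LSMeans, standard errors and intervals for Hb come from a model fitted "using the MMRM model (with compound symmetry [CS] for a variance-covariance matrix within subjects) similar to that used in" item (1). Those for Hb change are calculated "using the MMRM (with compound symmetry [CS] for a variance-covariance matrix within subjects". Neither has a fallback.

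SAP 7.5.2 (1), on the change to the Week 20/24 mean, says: "The analysis should be conducted using the MMRM model (with compound symmetry [CS] for a variance-covariance matrix within subjects". SAP 7.5.3 then names CS for efficacy analyses in general, the primary endpoint included, which conflicts with 7.5.1 (1). The CS wording recurs for other endpoints in 7.5.2 and for the subgroup LSMeans in 7.5.6 (1).

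On precision, SAP 7.1.1 says "Confidence interval (CI) will be 2-sided with a confidence coefficient of 95" percent, and Protocol 6.1 says "The number of subjects registered in the treatment period will be 20". Neither document gives an Hb SD by visit, a within-subject correlation or a dropout rate.

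**The concern.** CS assumes that Hb varies between subjects by the same amount at every visit and that any two visits are equally correlated. The design makes the first assumption doubtful, at least early on. Screening Hb is confined to 8.0 to <10.0 g/dL, the model adjusts for the first-day value, and everyone starts on 300 mg. Protocol 8.3 adds: "Dosage increases should be performed at intervals of at least 4 weeks in principle". Two weeks leave little time to diverge, whereas later doses may range from 150 to 600 mg.

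If variances differ, the model averages them, giving some visits intervals that are too wide and others intervals that are too narrow. Kenward-Roger adjusts for small samples but does not correct a wrong variance structure.

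There is also an internal mismatch. With the first-day value as covariate, modelling Hb or its change gives the same residuals; only the baseline coefficient shifts, by 1. The Week 20/24 mean and its change therefore deserve the same standard error, yet the plan starts one from unstructured and fixes the other at CS.

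**Working it through.** The plan states no SD, power or interval width, so there is no figure to reproduce.

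**Inputs from the documents.** n = 20 (Protocol 6.1); nine post-baseline visits, Weeks 2, 4, 6, 8, 10, 12, 16, 20 and 24 (Protocol 9.2.3); two-sided 95% intervals (SAP 7.1.1).

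**Assumptions.** Baseline-adjusted SDs of 0.5–1.0 g/dL at Week 2 and 0.7–1.2 at Week 24, and correlations of 0.6–0.9 at 4-week spacing.

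**Step 1: standard error under CS.** With complete data, SE = √(average of the visit variances / n) at every visit. For n = 20 this is 0.2236 × the pooled SD.

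**Step 2: one case by hand.** Let the SD rise linearly from 0.6 at Week 2 to 1.0 at Week 24. The nine variances sum to 5.477, so the average is 0.609 and the pooled SD 0.78.

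- CS standard error at every visit: 0.78/√20 = 0.174.
- Correct at Week 2: 0.6/√20 = 0.134. The ratio is 1.30, and normal-theory coverage is 2Φ(1.96 × 1.30) − 1 = 98.9%.
- Correct at Week 24: 1.0/√20 = 0.224. The ratio is 0.78, and coverage is 2Φ(1.96 × 0.78) − 1 = 87.4%.

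**Step 3: simulation.** 20,000 trials per scenario, with a baseline covariate and Satterthwaite degrees of freedom standing in for Kenward-Roger. Width is CS relative to a visit-specific interval.

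| Assumed SD (g/dL) | Width, Week 2 | Width, Week 24 | Coverage, Week 2 | Coverage, Week 24 |
|---|---|---|---|---|
| Flat 1.0 | 0.96–0.98 | 0.96–0.98 | 95% | 95% |
| 0.8 rising to 1.0 | 1.06–1.09 | 0.85–0.87 | 97% | 92% |
| 0.6 rising to 1.0 | 1.25–1.27 | 0.75–0.76 | 99% | 87–88% |
| 0.5 rising to 1.2 | 1.58–1.61 | 0.66–0.67 | 99.8% | 83% |
| 0.6, peak 1.1 at Weeks 8–10, then 0.8 | about 1.5 | 1.12–1.14 | 99.7% | 97–98% |
| 0.6, peak 1.1, then 0.95 | 1.53–1.57 | 0.97–0.99 | 99.7% | 95% |
| 1.0 falling to 0.7 | 0.84–0.86 | 1.21–1.23 | 91% | 98% |

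In the peak-then-0.8 case, Week 8 is the visit that is too narrow (coverage 90–91%). Square-root growth from 0.6 to 1.0 gives 99% and 89%. Visit-specific intervals covered 94.4–95.3% at Weeks 2 and 24 in every scenario.

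**Step 4: dropout.** Under CS with monotone dropout, the Week 24 standard error relative to Week 2 is 1.02–1.04 with 18 of 20 subjects left and 1.12–1.24 with 12. It grows only because fewer subjects are observed.

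**Step 5: the Week 20/24 change.** Take flat variance and correlation 0.85 per 2 weeks, decaying with the gap between visits. Weeks 20 and 24 then correlate at 0.85² = 0.7225. CS substitutes the average of 0.85^(gap/2) over all 36 visit pairs, which is 0.533. The CS standard error of the two-visit mean is √(1.533/1.7225) = 0.943 of the correct one, so coverage is about 2Φ(1.96 × 0.943) − 1 = 93.5%. With 0.80 per 2 weeks the ratio is √(1.438/1.64) = 0.936; with 0.90 it is √(1.652/1.81) = 0.955. Simulated coverage was 93–94% with flat variance and 91–92% with the SD rising from 0.8 to 1.0.

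**The case against.** The strongest reply is that late variance may not rise at all. Doses differ because they are titrated towards 10.0–12.0 g/dL. Protocol 8.3 raises the dose below 10.0, lowers it above 11.5 and interrupts it above 13.0. SAP 6.3 drops efficacy data from the day after rescue, and Protocol 12.1 allows withdrawal when Hb cannot be held in range. All of this works against a late spread. The reply stands: a reader might infer that the Week 24 interval is too narrow, but the documents do not establish that, and the table shows profiles where it is right or too wide. The reply does not rescue Week 2, where only a flat or falling profile avoids an over-wide interval.

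Second, the CS intervals are not the only inference. SAP 7.1.2 and 7.5.1 (2) also give descriptive means with SD and 95% CI at each visit, and paired t-tests, none of which use CS. The first-listed primary item starts from unstructured. This stands and limits the consequence. It also leaves two intervals for the same visit (Tables 14.2.2.1.1 and 14.2.2.2.1) without saying which prevails.

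Third, parsimony: unstructured over nine visits has 9 × 10/2 = 45 parameters against 2 for CS, with 20 subjects. In the subgroup models (ferritin or TSAT tertiles hold about 7 subjects each) a rich structure is not workable. This stands for the subgroups. For the full set, the SAP already accepts unstructured with an ordered retreat on the same data. The protocol's random-subject model (13.3.2) does imply CS, but SAP 7.5.1 (1) departed from it.

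**Conclusion.** The point holds in a conditional form. CS is fixed, without fallback or stated reason, for Hb and Hb change at each visit and for the Week 20/24 change, although the SAP ranks it last for the same data in 7.5.1 (1). If the variance of Hb differs by visit, the intervals are miscalibrated: about 99% coverage at Week 2 and 87–89% at Week 24 under an assumed SD rising from 0.6 to 1.0 g/dL, and none of that error under flat variance. Too wide at Week 2 is likely from the design; the direction at Week 24 is open. The shortfall to about 93–94% for the Week 20/24 change needs no change in variance, only correlation that decays with time.

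Two further inferences are not supported. Identical standard errors at every visit are exact only with complete data. And the argument from entry restriction and dosing concerns Hb; it does not show the same error for iron indices, EPO, lipids or QOL, and QOL has only two scheduled post-baseline visits. All SDs, correlations and dropout rates used here are assumptions.

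**What to change.** In SAP 7.5.1 (2) and 7.5.2 (1), replace the fixed CS with the ordered sequence already written in 7.5.1 (1). If one parsimonious structure is preferred throughout, use heterogeneous CS, which has 10 parameters (nine variances and one correlation), 8 more than CS. It cures the unequal-variance problem but still assumes a common correlation, so for the Week 20/24 change the full sequence is better. Reword 7.5.3 so that it no longer contradicts 7.5.1 (1). Keep a parsimonious structure for the subgroup models in 7.5.6 (1). State which interval is the reported one where descriptive and model-based results for the same visit differ.

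The cost is SAP wording and one program option. The downside is that more variance parameters are estimated from 20 subjects and some intervals may widen.

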8.5.3 Rescue therapy

The following rescue therapy options will be provided as needed for subject safety. Even if rescue therapies are performed, the subject can continue in the study unless investigators/subinvestigators determine study withdrawal is appropriate. Details of any rescue therapy implemented will be recorded in the subject's CRF.

(1) ESA formulations

If a subject has received maximum dosages of MT-6548 Tablets for ≥ 2 weeks and meets all criteria below, the investigator/subinvestigator may administer an ESA as a rescue therapy to improve Hb levels if necessary in order to secure subject safety. An ESA-based rescue therapy may also be provided without meeting the criteria below if the investigator/subinvestigator considers it necessary to secure subject safety, such as in cases of acute decreases in Hb levels. Administration of MT-6548 Tablets will be discontinued when an ESA-based rescue therapy is provided. Administration of MT-6548 Tablets may be resumed after an improvement in Hb levels and should not be coadministered with a rescue therapy with an ESA. Subjects who are not expected to resume administration of MT-6548 Tablets will be withdrawn from the study.

- ✓ Anaemia or anaemia symptoms (e.g., fatigue, weakness, shortness of breath, chest pain, confusion, dizziness) become aggravated compared to the first day of the treatment period to the point they are clinically problematic.
- ✓ Hb levels drop to < 8.0 g/dL.

(2) RBC transfusion

Usually, RBC transfusions are performed when clinically necessary in instances of acute or major bleeding. For less severe anemia, which may be exacerbated, or moderate to severe anemia symptoms, RBC transfusions may be performed as needed clinically at the discretion of the investigator/subinvestigator.

(3) Phlebotomy

Phlebotomy may be performed at investigator/subinvestigator discretion in cases of hyperviscosity syndrome, if the rate of Hb increase is concerning to investigators/subinvestigators, or if Hb levels are high enough to warrant concern to investigators/subinvestigators.

Rationale

Set out of consideration for subject safety.

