13.2 Data handling

(1) Definition of missing values

If test measurements are missing or if problems with samples etc. result in invalid measurements or reference values, these are handled as missing values.

(2) Handling of timepoint data for statistical summaries at each measurement timepoint

Statistical summaries for each evaluation timepoint will use data compliant with permitted ranges as described in “Table 9.1-1 Permitted ranges for study center visits.” There will be no supplementing with data from outside the permitted range.

If multiple data points exist within the permitted range, then the one closest to the scheduled day will be used. If there are deviations from the scheduled day, then data points prior to the scheduled day will be used for efficacy evaluation, and data points after the scheduled day will be used for safety evaluation.

(3) Handling of efficacy endpoints if rescue therapy was implemented

No data obtained after implementation of rescue therapy will be used for efficacy evaluation.

(4) Imputation of missing values

Missing values for treatment period Week 24 will be imputed by last observation carried forward (LOCF). Data from treatment period Week 24 with missing values imputed will be used as data from the completion of treatment period.

Required regulations for data handling other than those enumerated above will be described in the statistical analysis protocol prior to data lock.

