### **6.2 Handing of data for tabulation at each evaluation time point**

Data that meet the permitted range specified in the “Table 9.1-1 Permitted range of study visits” section of the protocol should be used for the tabulation at each evaluation time point and should not be imputed with those outside the permitted range.

If there are multiple data within the permitted range, then the one closer to the reference date should be adopted. If the deviations from the reference date are the same, data for the efficacy and safety evaluations should be adopted before and after the reference date, respectively.

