### **6.3 Handling of efficacy endpoints if rescue therapy is performed**

If rescue therapy is performed, data from the day after rescue therapy should not be used to assess efficacy.

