## 6.4 Imputation of missing values

The mixed repeated-measures model (MMRM) used to analyze the primary efficacy endpoint should not use data imputing missing data. If there are missing values at the first day of the treatment period, data from the day closest to the first day of the treatment period should be used as data for the first day of the treatment period.

For the primary endpoint, the mean Hb levels at Weeks 20 and 24 of the treatment period, missing data are imputed with data from the evaluation period immediately before the missing evaluation period (excluding the first day of the treatment period) (LOCF method). When any one evaluation time points has missing values, the data at the evaluation time point closest to the missing evaluation time point is adopted, and when two evaluation time points have missing values, the data in the two different evaluation time points closest to and before the missing evaluation time points should be adopted to calculate the mean Hb value. However, Hb values at the same evaluation time point should not be used.

In addition, clinical laboratory values, vital signs, and QOL indices among the efficacy endpoints, values imputed by the LOCF method at Week 24 of the treatment period should also be output. Data of Week 24 of the treatment period imputed with missing values will be used as data from the completion of treatment period.

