## 7.5 Efficacy analysis

As a general rule, efficacy analysis will be performed on the FAS. When necessary, descriptive statistics for continuous variables should be calculated and frequency and proportion will be calculated for discrete variables. No data from the day after the rescue therapy implementation date should be included in the efficacy analysis.

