The time course diagram should be prepared for mean Hb values at each evaluation time point in the treatment period. 95% CI of the mean will be represented by an error bar. The time course diagram should be prepared for Hb values at each evaluation time point of the treatment period in each subject.

(3) Proportion of subjects with mean Hb levels within the target range (10.0–12.0 g/dL), <10.0 g/dL, and ≥12.0 g/dL at each time point of the treatment period

The number, proportion, and 95% CI (Clopper-Pearson [Exact] method) of the proportion of subjects with Hb value within the target range (10.0 to <12.0 g/dL, within), <10.0 g/dL (below), and ≥12.0 g/dL (above) at each time point of the treatment period should be provided. Before and after comparison should be conducted for changes from the first day of the treatment period to each evaluation time point using the McNemar test.

The proportion of subjects in each Hb category (within the target range [10.0 to <12.0 g/dL], <10.0 g/dL, and ≥12.0 g/dL) at each evaluation time point of the treatment period should be provided as a stacked bar graph assuming that the number of subjects at each evaluation time point is 100%. Stacked bar charts should be separately prepared.

(4) Number of days from the first day of the treatment period required to reach the target Hb range (10.0 g/dL to <12.0 g/dL)

Descriptive statistics should be calculated for number of days required from the first day of the treatment period to reach target Hb range (10.0 g/dL to <12.0 g/dL). The number of days should be calculated as the first evaluation date reached target Hb range – first date of the treatment period

+ 1. If target Hb range is not reached, the final date of evaluations – first date of the treatment period + 1 should be assumed.

A Kaplan-Meier plot should be shown for days from the first day of the treatment period required to reach the target Hb range.

No subjects with an Hb value of  $\geq 10.0$  g/dL on the first day of the treatment period will be included in the calculation.

(5) Hb value increase rate

Descriptive statistics should be calculated for the Hb value increase rate (g/dL/week).

The Hb value increase rate should be analyzed by 2 methods defined in the “Hb value increase rate”.

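### Subjects rescued or withdrawn for loss of Hb control leave the target-range bars, and by inference the tables, instead of counting as not in range; one all-FAS sensitivity analysis would show the effect

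*SAP*

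**What the plan says.** SAP 7.5.1(3), listed under the primary endpoint, asks at each visit for the number, proportion and exact 95% CI of subjects with Hb within range (10.0 to <12.0 g/dL), below 10.0 and at or above 12.0. In the accompanying figure the category proportions "should be provided as a stacked bar graph assuming that the number of subjects at each evaluation time point is 100" per cent. The table has no stated denominator beyond the general rule in SAP 7.5 that efficacy uses the FAS. SAP 7.5.2(2) is similar: "The number, proportion, and 95% CI (Clopper-Pearson [exact] method) of the proportion of subjects with a mean Hb increase of" at least 1.0 g/dL, again with no per-visit denominator.

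These provisions decide which values reach a visit:

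- SAP 6.3: "data from the day after rescue therapy should not be used to assess efficacy". SAP 7.5 repeats it: "No data from the day after the rescue therapy implementation date should be included in the efficacy analysis".
- SAP 6.2: visit data must lie in the permitted window and "should not be imputed with those outside the permitted range".
- Protocol 8.5.3: a rescued subject may stay in the study, but one given an ESA who is not expected to go back to study drug is withdrawn.
- Protocol 12.1(4): inability to control Hb in the target range is an example of a ground for withdrawal.

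On Week 24, protocol 13.2(4) says "Missing values for treatment period Week 24 will be imputed by last observation carried forward (LOCF"), and protocol 13.3 exempts only the MMRM. SAP 6.4 says that for laboratory values among the efficacy endpoints "values imputed by the LOCF method at Week 24 of the treatment period should also be output". The output list in the SAP errata labels the target-range table (14.2.2.4.1) and the 1.0 g/dL table (14.2.3.2.1) FAS only. Other Hb tables, such as the Week 20 and 24 average (14.2.1.1.1) and Week 24 Hb by site (14.2.4.1), are labelled LOCF, FAS.

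**The concern.** A subject whose Hb control fails badly enough to need an ESA or a transfusion, or to be withdrawn, has no usable Hb at later visits. The three categories have no place for that subject. On the natural reading of the bar rule, the subject leaves both numerator and denominator, so losing Hb control can remove a subject from the measure of Hb control.

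The study is uncontrolled, so no comparator undergoes the same loss and the proportion is read at face value. With a target of 20 subjects, a few losses move it visibly. The SAP does address non-achievers in the next item: 7.5.1(4) assigns a value to a subject who never reaches range. Item (3) has no matching rule.

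**Working it through.** The plan has no figure to reproduce. The 20 subjects rest on feasibility (protocol 6.1, SAP 2.3), with no expected proportion, rescue rate or dropout rate.

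**Inputs.** N = 20 is from the documents, taken here as the FAS. The CI method (Clopper-Pearson, two-sided 95%) is from SAP 7.1.1 and 7.5.1(3). The following are assumptions: x = 12 observed in range, k subjects without usable Hb at the visit, and f of those k truly not in range.

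**Formulas.** Observed cases: x/(N − k). All-FAS truth: (x + k − f)/N, which equals x/N when all the lost are failures (f = k).

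**Number lost, all failures (x = 12):**

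| k | Observed cases (95% CI) | Counted as not in range (95% CI) | Difference |
|---|---|---|---|
| 1 | 12/19 = 63.2% (38.4–83.7) | 12/20 = 60.0% (36.1–80.9) | 3.2 points |
| 2 | 12/18 = 66.7% (41.0–86.7) | 60.0% | 6.7 points |
| 4 | 12/16 = 75.0% (47.6–92.7) | 60.0% | 15.0 points |

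Over k = 1 to 6 and x = 10 to 14 the difference runs from 2.6 points (10/19 against 10/20) to 30.0 points (14/14 against 14/20). The upper end needs six losses, all failures, with every remaining subject in range.

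**Direction (k = 4, observed 75%).** The all-FAS truth is (16 − f)/20.

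| f | Truth | Observed minus truth |
|---|---|---|
| 4 | 60% | +15 points |
| 3 | 65% | +10 points |
| 2 | 70% | +5 points |
| 1 | 75% | 0 |
| 0 | 80% | −5 points |

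**Week 24 if LOCF applies.** With four lost failures, j of whom have a last usable value in range, the result is (12 + j)/20: 60%, 65%, 70%, 75% or 80% for j = 0 to 4. These cases are not equally likely. Under the standard ESA criteria, one condition is "Hb levels drop to < 8.0 g/dL". A usable central-laboratory Hb on or just before that rescue would usually be below range, so LOCF would class the subject correctly. Protocol 8.5.3 also allows discretionary ESA rescue for an acute fall, where the last scheduled value may still be in range.

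**When losses can start.** From 300 mg, two one-tablet steps reach 600 mg. Steps are in principle at least 4 weeks apart, and the standard criteria then need at least 2 weeks at maximum. Steps at Weeks 4 and 8 give Week 10; steps at Weeks 2 and 6 give Week 8. Before then, losses come mainly from discretionary rescue, transfusion, phlebotomy or withdrawal.

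**The test.** The McNemar comparison depends only on subjects who change category. Dropping someone out of range at both times leaves it unchanged. The issue is therefore mainly with the estimated proportion.

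**The case against.** Several counterpoints have force.

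- **The denominator can mostly be recovered.** The three counts add up to the subjects with usable Hb, and 12 (75.0%) can only be 12/16. With FAS N in the disposition table, a reader can compute 12/20. This stands: a missing denominator alone is a labelling matter. It does not tell the reader which of the missing lost Hb control.
- **The 100 per cent rule governs a figure.** Extending it to the tables is an inference, and I treat it as one.
- **Other outputs give visibility.** Rescue is tabulated by visit interval (SAP 7.5.2(3)), discontinuation by reason (7.2.2), and Hb is plotted per subject (7.5.1(2)). These help, but none of the table descriptions combines rescue with in-range status. The figure and listing contents are not in the text available, so a subject-level cross-reference cannot be excluded.
- **Counting rescue as failure has its own bias.** Protocol 8.5.3 describes transfusion mainly for acute or major bleeding, which need not mean loss of drug effect, and a rescued subject may resume study drug and regain control. This stands, and is why the added analysis should be a sensitivity analysis.

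A reader might infer that the reported proportion will be inflated by some 15 points. The documents do not support that. It needs four of 20 lost, all failures, and many withdrawal grounds are unrelated to Hb. Nor is excluding post-rescue values itself an error; it is a legitimate rule that lacks a status for the subjects it removes.

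**Conclusion.** The concern holds as a gap in the plan, not as a demonstrated bias. Followed as written, the bars drop subjects after ESA or transfusion rescue, or after withdrawal for uncontrolled Hb, instead of counting them as not in range. The tables in 7.5.1(3) and 7.5.2(2) probably do the same. Inflation is plausible if most losses reflect failed control. Under the assumptions above it is about 3 to 7 points with one or two losses, small against a CI of roughly ±22 points, and 15 points with four. Understatement by 5 points is also possible.

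At Week 24 it would be too strong to say that no imputation is planned. The FAS-only labels suggest observed cases, but protocol 13.2(4) and SAP 6.4 provide LOCF values, and the passages need reconciling. LOCF would reduce the problem in many standard-criteria rescues without acting as a failure rule.

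**What to change.** In SAP 7.5.1(3) and 7.5.2(2):

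1. Keep the planned observed-case result, state its denominator, and show n with data beside FAS N at each visit.
2. State whether the Week 24 row is observed or LOCF, and reconcile this with protocol 13.2(4), SAP 6.4 and the table labels.
3. Add one sensitivity analysis with all FAS subjects as denominator. Count subjects with earlier ESA or transfusion rescue, or withdrawn for uncontrolled Hb, as not in range or non-responder. Classify the withdrawals before data lock. State one rule for subjects missing for other reasons, including those whose data stop after phlebotomy.

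If data are already locked, protocol 13.4 allows the addition with reasons given and results kept distinct from the original plan.

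The cost is SAP wording, a derived flag and two added tables. Rescue details and withdrawal reasons already go into the CRF (protocol 8.5.3, 12.2). The documents do not show whether the CRF separates uncontrolled Hb from other reasons, so some judgement is needed. The added analysis will tend to give somewhat lower proportions, and may be biased downward where transfusion was for bleeding or the subject later regained control.
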